#### STUDY DESIGN

This is a two-group, active-control, RCT of the KIU! an online intervention. Participants will be randomized to two groups in equal proportions (KIU! condition n=450; control arm n=450). The KIU! intervention involves 7 modules completed across three sessions, done at least 24 hours apart (i.e., at least 3 days), and totaling ~2 hours to content. Across these modules, the KIU! intervention uses diverse delivery methods (e.g., videos, animation, games) to address HIV knowledge, motivate safer behaviors, teach behavioral skills, and instill self-efficacy for preventive behaviors. The control condition contains the same number of modules as the KIU! condition, with the same requirement to participate across three sessions. It reflects HIV information that is currently available on many websites so as to understand how the KIU! intervention improves upon what is currently available online. Booster sessions will be delivered at 3 and 6 months for each arm.

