B.12. Power and Sample Size. All power calculations were performed in R version 2.14.0 and using common sample size formula for repeated measures with nominal Type I error rates (i.e.  $\alpha$ =.05) and effect estimates based on our preliminary studies. We will screen approximately 4500 YMSM, enroll 900 YMSM, and assume 80% retention based on our preliminary studies. Assuming participants are randomized to two groups in equal proportions, we will have 97% power to detect a 11% reduction in the rate of unprotected sex (ERR = 0.89) due to the intervention, assuming the correlation between repeated measures is 0.8. The correlation among repeated measures plays an important role in the calculation; in this case, our power calculation is conservative if the correlation among repeated measures is, in fact, weaker than 0.8. The smallest effect size with which we will have 80% power to detect is a 6.5% reduction in the rate of unprotected sex. Technically speaking, our study will have greater power than what is reported here after we adjust for our blocked design. In conclusion, we will have 80% power to detect an effect size equal to half of what we observed in our pilot trial and less than half of the lower bound of effect sizes seen in other HIV prevention programs with MSM. For our primary biomedical endpoint of STI incidence, we assume the annual incidence based on our longitudinal cohort studies in the range of 10 to 15%. If the incidence rate in the control group is 10%, we will have 81%, 70%, and 56% power to detect an incidence reduction of 7%, 6%, and 5%, respectively. If the incidence rate in the control group is higher, say 15%, then the power reduces to 71%, 60%, and 47%, respectively. The objective of aim 3 is to estimate the intervention effect among subgroups and test for significant differences. In data analyses, this will be achieved by testing 2-way interactions, treatment by subgroup. For a conservative power calculation, we repeated the power calculations as per aim 1 with a reduced sample size. Assuming N=200 per group (say, for racial/ethnic subgroups), an ERR=0.89 as above, and strong correlation among repeated measures (i.e. 0.8), we will have 91%, 85%, and 77% power to detect a 10%, 9%, and 8% reduction in the rate of unprotected sex among YMSM, respectively, due to KIU! intervention. The power will be less for effect sizes more subtle than 8% and less for smaller subgroups. In addition to racial/ethnic subgroups, other subgroups of interest include sexual orientation identity groups (81% gay, 17% bisexual identified) and relationship groupings (30% recent serious relationships). The power for each subgroup comparison will be similar to the power described above.

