#### C. HUMAN SUBJECTS

## C.1. RISKS TO HUMAN SUBJECTS

**C.1.a.** Human Subjects Involvement, Characteristics, and Design. We will screen 4532 ethnically diverse 18–29 year-old young men who have sex with men (YMSM) following an HIV negative test result from community clinics in Chicago, New York, and Atlanta or at a university site (Emory and Hunter). (This total sample includes 12 YMSM who will participate in acceptability and usability testing prior to implementation.) About 20% of these young men (n = 900) are anticipated to enroll into and complete the study. Investigators with a history of successfully conducting HIV behavioral research will be supervising research in these cities. Three academic institutions (Northwestern University, Hunter College, and Emory University) with exemplary human subjects protection programs will be involved in participant recruitment. The investigative team has extensive experience conducting research and providing services to YMSM. The Principal Investigator has been a member of the Institutional Review Board (IRB) and has expertise in ethical issues related to conducting research with sexual minority youth.

MSM will range in age from 18-29 years, consistent with findings regarding emerging adulthood as a period of heightened risk for STIs/HIV among MSM. We will recruit a racially and ethnically diverse sample, representing both high-risk YMSM in Chicago, Atlanta, and New York, as well as the demographics of the population seeking services at each recruitment site. As described in the research design, the size and epidemiologic trends of the HIV/AIDS epidemic in each city make them good candidates for conducting an RCT among YMSM. These cities represent distinct geographical regions (i.e. Midwest, Southeast, East Coast) with notable differences in population demographics and culture. This diversity will allow examination of whether the intervention works equally well in a variety of urban settings, thus increasing our ability to draw conclusions about the generalizability of findings. Given site-specific recruitment patterns, we will readily achieve representation across White, Black, and Latino groups, but we will also stratify enrollment to equal 1/3 for each group). Each site will screen approximately 1250 YMSM and enroll approximately 250 YMSM.

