- b) Randomize participants to either the highly interactive and engaging KIU! intervention or an HIV knowledge condition similar to existing web-based HIV educational materials.
- c) Measure intervention outcomes through 12 months post-intervention. The primary behavioral outcome will be the count of unprotected anal sex acts and the primary biomedical outcome will be STI incidence. Additional behavioral outcomes include: alcohol and drug use prior to sex, risky sex after substance use, condom errors, IMB factors, and receipt of an HIV test. We will test for dose effects and decay in intervention effects over time.

Aim 3: Explore if the KIU! intervention has differential efficacy across important sub-groups of YMSM. We will explore moderators of intervention effects by testing for significant differences in the magnitude of intervention effects based on the types of substances used prior to sex, as well as race/ethnicity, relationship status, and gay/bisexual identity. These findings will be used to assist in future targeting of KIU! delivery and identify need for further intervention tailoring.

A2. Study design.

This is a two-group, active-control, RCT of KIU!, an online intervention. Participants will be randomized to two groups in equal proportions (KIU! condition n=375; control arm n=375). The KIU! intervention involves 7 modules completed across three sessions (See Table 1 for module descriptions),done at least 24 hours apart (i.e., at least 3 days), and totaling ~2 hours to content. An innovative aspect of KIU! is that each module is based on a particular setting or situation relevant to the lives of YMSM, with developmentally appropriate health behavior change content embedded within each of these settings. Module content is designed to be

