All power calculations were performed in R version 2.14.0 and using common sample size formula for repeated measures²¹⁰ with nominal Type I error rates (i.e. α =.05) and effect estimates based on our preliminary studies. We will screen approximately 4500 YMSM, enroll 900 YMSM, and assume 80% retention based on our preliminary studies. Assuming participants are randomized to two groups in equal proportions (KIU! condition n=375; control arm n=375), we will have 97% power to detect a 11% reduction in the rate of unprotected sex (ERR = 0.89) due to the intervention, assuming the correlation between repeated measures is 0.8. The correlation among repeated measures plays an important role in the calculation; in this case, our power calculation is conservative if the correlation among repeated measures is, in fact, weaker than 0.8. The smallest effect size with which we will have 80% power to detect is a 6.5% reduction in the rate of unprotected sex. Technically speaking, our study will have greater power than what is reported here after we adjust for our blocked design. In conclusion, we will have 80% power to detect an effect size equal to half of what we observed in our pilot trial and less than half of the lower bound of effect sizes seen in other HIV prevention programs with MSM²⁶. For our primary biomedical endpoint of STI incidence, we assume the annual incidence based on our longitudinal cohort studies in the range of 10 to 15%. If the incidence rate in the control group is 10%, we will have 81%, 70%, and 56% power to detect an incidence reduction of 7%, 6%, and 5%, respectively. If the incidence rate in the control group is higher, say 15%, then the power reduces to 71%, 60%, and 47%, respectively. The objective of aim 3 is to estimate the intervention effect among subgroups and test for significant differences. In data analyses, this will be achieved by testing 2-way interactions, treatment by subgroup. For a conservative power calculation, we repeated the power calculations as per aim 1 with a reduced sample size. Assuming N=200 per group (say, for racial/ethnic subgroups), an ERR=0.89 as above, and strong correlation among repeated measures (i.e. 0.8), we will have 91%, 85%, and 77% power to detect a 10%, 9%, and 8% reduction in the rate of unprotected sex among YMSM, respectively, due to KIU! intervention. The power will be less for effect sizes more subtle than 8% and less for smaller subgroups. In addition to racial/ethnic subgroups, other subgroups of interest include sexual orientation identity groups (81%

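### The two power figures for the primary behavioural outcome cannot both hold for one design, and the SAP ties them to 375 per arm while enrolling 900

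*SAP*

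**What the plan says.** SAP A.5 and Protocol B.12 carry the same power paragraph. It sets alpha at 0.05 without giving sidedness, enrolment at 900, retention at 80% and the correlation between repeated measures at 0.8. It then states that "we will have 97% power to detect a 11% reduction in the rate of unprotected sex (ERR = 0.89) due to the intervention". Two sentences later, with no change of sample size, variance or correlation, it adds that "The smallest effect size with which we will have 80% power to detect is a 6.5% reduction in the rate of unprotected sex".

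The same paragraph gives power for Aim 3: "Assuming N=200 per group (say, for racial/ethnic subgroups), an ERR=0.89 as above" and correlation 0.8, "we will have 91%, 85%, and 77% power to detect a 10%, 9%, and 8% reduction in the rate of unprotected sex among YMSM". It does not say whether 200 is per arm or per subgroup.

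On sample size, SAP A.5 inserts "KIU! condition n=375; control arm n=375" into the sentence giving the 97%, and SAP A2 prints the same numbers. Protocol B.12 has no per-arm number. The Protocol's Study Design section gives "KIU! condition n=450; control arm n=450". Protocol C.1.a anticipates 900 enrolled, yet says: "Each site will screen approximately 1250 YMSM and enroll approximately 250 YMSM".

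**The concern.** With sample size, variance and alpha fixed, one power statement determines every other point on the power curve. Two statements for one design must therefore lie on the same curve, and these two do not appear to.

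This is the primary behavioural outcome. As written, a reader cannot tell whether the trial was designed to detect a 6.5% reduction or one of about 8% with 80% power. Nor can the reader tell whether the figures belong to 750 or 900 participants, enrolled or retained. That sensitivity is the yardstick against which a null result would be read.

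**Working it through.** **Inputs.** From SAP A.5 and Protocol B.12: alpha 0.05; 97% at 11% (rate ratio 0.89); 80% at 6.5%; correlation 0.8; 900 enrolled; 80% retained. Sidedness, baseline rate, dispersion and number of repeated measures are not stated. I assume a two-sided test first and use both the linear scale and the log-rate scale.

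**Formula.** effect / SE = z_alpha + z_power. At a fixed SE, the ratio of two effects must equal the ratio of their z-sums, so baseline rate, dispersion and n cancel.

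**The stated pair**
- z-sums: 1.960 + 1.881 = 3.841 for 97%; 1.960 + 0.842 = 2.802 for 80%. Required ratio 3.841 / 2.802 = 1.37.
- Stated ratio: 11 / 6.5 = 1.69 (linear); 0.1165 / 0.0672 = 1.73 (log).
- Implied SE, log: 0.1165 / 3.841 = 0.0303 and 0.0672 / 2.802 = 0.0240, a variance ratio of 1.60. Linear: 0.0286 and 0.0232, ratio 1.52.

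| Taken as correct | 80%-power reduction | Power at 6.5% | Power at 11% |
|---|---|---|---|
| 97% at 11% | 8.0-8.1% | 60-62% | 97% |
| 80% at 6.5% | 6.5% | 80% | 99.7-99.8% |

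**Possible reconciliations**
- One-sided alpha: z-sums 3.526 and 2.486, ratio 1.42. From 97% at 11%, power at 6.5% is 65-67%; from 80% at 6.5%, power at 11% is 99.5-99.6%.
- Rounding: with each number at the edge of its rounding, the z-sum ratio is at most 1.41 and the effect ratio at least 10.5 / 6.55 = 1.60.
- The 97% at 375 per arm and the 80% at 450: detectable reduction 7.3-7.5%, not 6.5%.
- A weaker correlation for the 6.5% figure: with design effect (1 + (m - 1) x rho) / m, absorbing the 1.52-1.60 needs rho of about 0.31-0.35 (m = 3) or 0.38-0.41 (m = 4). Only 0.8 is assumed anywhere.

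**Aim 3 figures as a cross-check.** On the log scale, 91%, 85% and 77% at 10%, 9% and 8% imply SEs of 0.0319, 0.0315 and 0.0309, so they agree closely with one another. Scaling by sqrt(200 / n):
- N = 200 per arm: 97% at 11% needs only 207-224 per arm; 80% at 6.5% needs 326-354. At 360 per arm the detectable reduction is 6.2-6.5% and power at 11% is at least 99.8%. At 300 per arm (750 x 80% / 2) these are 6.8-7.0% and 99.4-99.6%.
- N = 200 for the whole subgroup (100 per arm): at 360 per arm, 4.4-4.6% and over 99.9%.

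The 97% conflicts with the Aim 3 figures on either reading. The 6.5% fits them only on the per-arm reading.

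**Sample size**
- 375 + 375 = 750, against 900 enrolled. The 375 is not the retained number: the SAP calls these participants randomized, and 900 x 80% / 2 = 360.
- 3 x 250 = 750 enrolled, against 900. 3 x 1250 = 3750 screened, against about 4500. The recruitment cells in the SAP B.2 timetable sum to 450 + 3 x 660 + 2 x 1035 = 4500.

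**Why dispersion must be stated.** Illustration only, on assumptions not in the power section: Poisson-type variance, the pilot control mean of 6.2 (Protocol B.3, Table 1), three follow-ups, correlation 0.8, 360 per arm. For dispersion 1, 2 and 5, power at 11% is 98%, 82% and 44%, and the detectable reduction is 7.7%, 10.7% and 16.7%.

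**The case against.** The arithmetic on the pair is not in dispute. The best case on the other side concerns what it shows and how much it matters.

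- **Which figure is wrong is open.** The illustrative Poisson run at dispersion 1 gives 98% at 11% and 7.7% detectable, which favours the 97% over the 6.5%. The Aim 3 figures point the other way, but only with N = 200 read as retained per arm do they land near 6.5%. If it means enrolled per arm (160 retained), scaling to 360 gives 5.5-5.8%. This stands, and I do not name the wrong figure.
- **The two figures may come from two designs.** If 97% belongs to 300 per arm, scaling to 450 gives a detectable reduction of 6.55% (linear) or 6.7% (log). That is close, but it sets the retained number of a 750-person trial against the enrolled number of a 900-person trial. The text states no such switch, and 97% at 300 per arm still conflicts with Aim 3.
- **The trial size is clear elsewhere.** Enrolment is 900 throughout both documents, and the 375, 250 and 1250 look like remnants of a 750-person design. That is likely, but they are current text, and the SAP places 375 inside the power sentence itself.
- **The consequence is limited.** What a null result excludes comes from the confidence interval, not from planning power, and on either stated figure power at 11% is about 97% or more. Both points are fair. They bear on the consequence and leave the contradiction in place.
- **360 per arm is not the only defensible input.** The analysis uses all available measurements, so completers understate the information. This stands, but 360 follows from the plan's own retention assumption.

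**Conclusion.** The concern holds. For one sample size, variance and alpha, 97% at 11% and 80% at 6.5% contradict each other by a factor of 1.52-1.60 in variance or sample size. In practical terms the plan's 80%-power sensitivity is either 6.5% or about 8%. This rests on the usual normal approximation and on no assumed baseline rate or dispersion; sidedness and rounding do not rescue it. The 375 per arm, 250 per site and 1250 screened per site are wrong as printed against 900 enrolled, 450 per arm and about 4500 screened.

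The documents do not show which power figure is in error or that the trial is underpowered. The correction should be made, but it concerns the stated assumptions and not the size of the trial.

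**What to change.** - In SAP A2 and A.5, replace 375/375 with 450/450. In Protocol C.1.a, replace 250 enrolled per site with 300 and 1250 screened per site with 1500. Protocol B.10(a) plans equal enrolment across the three cities.
- Rerun the calculation once at 360 retained per arm with correlation 0.8. State sidedness, baseline rate, dispersion and number of repeated measures. If another effective sample size is preferred because partial follow-up is used, state and justify it.
- Report the power at 11% and the reduction detectable with 80% power from that one run, identically in SAP A.5 and Protocol B.12.
- Take the Aim 3 figures from the same inputs, and say whether N = 200 is per arm or per subgroup, and enrolled or retained.
- Replace the claim that "we will have 80% power to detect an effect size equal to half of what we observed in our pilot trial" with the recomputed reduction. Half of the pilot's 44% is 22%, far larger than 6.5%, so the sentence is imprecise, though not contradictory.

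The cost is one rerun and wording changes in four sections, with no added participants. The stated power may move in either direction.

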
gay, 17% bisexual identified) and relationship groupings (30% recent serious relationships). The power for each subgroup comparison will be similar to the power described above.

B. Trial Management

B1. List of participating enrolling clinics or data collection centers.

This interdisciplinary and multisite project requires participation of multiple institutions in order to accomplish the aims of the project. Recruitment of the requisite sample of diverse YMSM and the aim to understand the generalizability of the intervention across diverse settings requires the participation of institutions in multiple cities. The Chicago site will be led by the Principal Investigator (PI), [name], at Northwestern University (NU) in Chicago, IL. The following community-based organizations (CBOs) in Chicago will be participating in recruitment of participants: Center on Halsted, Broadway Youth Center and Howard Brown Health Center, and Vida/SIDA (a project of the Puerto Rican Cultural Center). The New York site will be led by Co-Investigator, [name], Professor at Hunter College of the City University of New York (CUNY) and the founder and Co-Director of Center for HIV/AIDS Educational Studies and Training (CHEST) of Hunter College. The following CBOs in New York will be participating in recruitment of participants: Gay Men of African Descent, Gay Men's Health Crisis, Hispanic AIDS Forum, Harlem United, and Callen Lorde Community Health Center. The Atlanta site will be led by Co-Investigator, [name], Associate Professor at Emory University. The following CBOs in Atlanta will be participating in recruitment of participants: AID Atlanta, AID Gwinnett, and Someone Cares.

B.2. Projected timetable.

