We will screen approximately 4500 YMSM to enroll an ethnically diverse sample of YMSM between the ages of 18 and 29 (N= 900). Participants will represent an equal proportion of Black, Latino, and White YMSM, consistent with both high-risk YMSM populations in each city, as well as the demographics of the population seeking services at each recruitment site. The majority of participants will be those who engage in substance use prior to sex. Based on our KIU! pilot data, over 50% of YMSM reported drug and/or alcohol use before sex. The team in each city has assembled a cadre of CBOs whose indigenous staff will recruit YMSM upon a negative HIV test result. We have partnered with CBOs for recruitment in order to maximize our ability to test the intervention under conditions in which it would eventually be disseminated.

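### Aim 3 is tested by treatment-by-subgroup interactions, but the stated 91/85/77% power is for an effect inside one subgroup, and power is not similar for each subgroup comparison.

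*SAP*

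**What the plan says.** SAP A.5 and Protocol B.12 carry almost the same paragraph. The Aim 3 objective there has two parts: to estimate the effect in subgroups and to test whether subgroups differ. For the testing, "this will be achieved by testing 2-way interactions, treatment by subgroup"; SAP C3 and Protocol B.11 repeat that moderator-by-group interactions will be tested.

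The power basis is: "For a conservative power calculation, we repeated the power calculations as per aim 1 with a reduced sample size". The size is given as "Assuming N=200 per group (say, for racial/ethnic subgroups), an ERR=0.89 as above", with a repeated-measures correlation of 0.8, and the result is 91%, 85% and 77% power for reductions of 10%, 9% and 8% due to the intervention.

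The paragraph then warns: "The power will be less for effect sizes more subtle than 8% and less for smaller subgroups". It goes on to list identity groups (81% gay, 17% bisexual) and relationship groups (30% in recent serious relationships), and closes: "The power for each subgroup comparison will be similar to the power described above".

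On sample size, the SAP enrols 900 with 80% retention but gives the arms as "KIU! condition n=375; control arm n=375", which totals 750. The Study Design section of the Protocol says "Participants will be randomized to two groups in equal proportions (KIU! condition n=450; control arm n=450"). SAP B.3 adds: "Participants will represent an equal proportion of Black, Latino, and White YMSM".

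**The concern.** The test that is planned and the test that is powered are different. An interaction compares two subgroup effects, and its variance is the sum of their variances. A main-effect calculation at a subgroup's sample size leaves out the second variance, so calling it conservative is wrong for the interaction.

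The closing sentence also contradicts the caveat just before it. Power cannot fall in smaller subgroups and still be similar for a 17% subgroup.

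N=200 is ambiguous. Earlier in the paragraph the groups are the trial arms, but the example given is racial/ethnic subgroups.

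Protocol A.4 and Aim 3 in SAP A1 would use subgroup differences to target the intervention and to identify where it needs tailoring. A reader who takes 77–91% as the chance of detecting such differences could read a non-significant interaction as evidence that the intervention works equally well across race, identity and relationship groups. Neither document says how a non-significant interaction will be interpreted.

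**Working it through.** **Inputs.** From SAP A.5: alpha 0.05 (taken as two-sided), 91/85/77% power for 10/9/8% reductions at N=200, 900 enrolled, 80% retained, and shares of 81% gay, 17% bisexual and 30% serious relationship. From SAP B.3: one third in each racial/ethnic group. Assumed: equal allocation, equal variance across subgroups, and subgroup differences of 10, 9 and 8 percentage points, because no interaction effect is stated.

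**Reproducing the plan's figures.** The documents give no baseline rate, dispersion or number of measurements for the power formula, so the figures cannot be rebuilt from first principles. They can be inverted with power = Φ(δ/SE − 1.960):

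- 0.10/(1.960 + 1.341) = 0.0303
- 0.09/(1.960 + 1.036) = 0.0300
- 0.08/(1.960 + 0.739) = 0.0296

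A common SE of 0.0300 returns 91.5/85.1/76.0%, so the three figures agree with one another as power for a single effect at N=200.

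**Interaction at the plan's own N.** With N=200 in both subgroups, SE = 0.0300 × √2 = 0.0424, and power is 65/56/47%. This is the same whichever way N=200 is read.

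**Expected subgroup sizes.** Retained per arm: 900 × 0.8 / 2 = 360. That gives 120 per race group, 291.6 gay, 61.2 bisexual, 108 serious and 252 other.

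**Scaling.** With n per arm, SE(within) = 0.0300 × √(K/n) and SE(interaction) = 0.0300 × √(K/n₁ + K/n₂). K = 200 if N=200 means per arm, and K = 100 if it means the whole subgroup. For example, gay versus bisexual with K = 200: 0.0300 × √(200/291.6 + 200/61.2) = 0.0597, and Φ(0.10/0.0597 − 1.960) = 39%.

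Power (%) for 10/9/8 points, 720 analysed:

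| Comparison | 200 = per arm | 200 = whole subgroup |
|---|---|---|
| Within one race group | 73/64/54 | 95/91/83 |
| Within serious relationship | 69/60/50 | 93/88/79 |
| Within bisexual | 45/38/31 | 74/65/55 |
| Within gay | 98/95/90 | all above 98 |
| Within other relationship | 96/92/85 | all above 98 |
| Interaction, two race groups | 45/38/31 | 73/64/54 |
| Interaction, gay vs bisexual | 39/33/27 | 66/57/47 |
| Interaction, serious vs other | 54/45/37 | 83/74/64 |

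**Difference detectable with 80% power** (2.80 × SE), in the order race pair, gay vs bisexual, serious vs other: about 15, 17 and 14 points if per arm; about 11, 12 and 10 if whole subgroup.

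**Sensitivity.** Working with the log rate ratio moves these powers by about one percentage point at most. If only 750 were randomised (600 retained), gay versus bisexual under the per-arm reading falls to 33/28/23%.

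**The case against.** The strongest reply is that the figures are incomplete rather than miscalculated. Half of the Aim 3 objective is to estimate effects within subgroups, within-subgroup power bears on that half, and the text says openly that it reran an earlier calculation. If N=200 is the whole subgroup, race groups and serious relationships meet or exceed 91/85/77% within subgroup. That reading has support: 750 × 0.8 / 3 = 200, whereas 200 per arm in three race groups would need 1,200 men. This stands, and it narrows the within-subgroup shortfall under that reading to bisexual men. It does not help the interactions.

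The mixed model uses all available measurements, so 720 is a cautious count. With all 900 fully analysed and the whole-subgroup reading, serious versus other reaches 90/83/74%, which could fairly be called similar. Under the same assumptions the race pair is 82/74/64% and gay versus bisexual 75/67/56%, so the claim for each comparison still fails.

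The absolute figures depend on a back-solved SE, and the Aim 2 statements imply other values: 0.11/(1.960 + 1.881) = 0.0286 and 0.065/(1.960 + 0.842) = 0.0232 for the whole trial. Those two disagree with each other. Scaled from 360 to 120 per arm for a race pair (× √6), they give 30% or 42% power at 10 points, no higher than the values above. The uncertainty is real but does not rescue the claim. The 750-randomised case is also doubtful, since SAP A.3 refers to 900 men enrolled; it is a lower bound only. Race has three levels, so a pair is one contrast within a two-degree-of-freedom test.

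Finally, Aim 3 is labelled exploratory and the paragraph already warns about small subgroups. That lowers the stakes without making the closing sentence true.

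**Conclusion.** The concern holds. The stated 91/85/77% is within-subgroup power at N=200, no interaction power is given, and the sentence claiming similar power for each comparison is wrong under either reading of N=200. With 720 analysed, the named interaction contrasts have 39–83% power at a 10-point difference and 27–64% at 8 points, against the stated 91% and 77%. Bisexual men fall short even for a within-subgroup effect.

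The exact percentages assume the SE implied by the plan's own triplet, equal variances, equal allocation and subgroup differences of 8–10 points. Two conclusions do not depend on that SE: variances add in an interaction, and precision falls with subgroup size. Larger differences, of roughly 10 to 17 points, would be detectable with 80% power. This corrects a stated figure for an exploratory aim and leaves the design unaffected.

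**What to change.** In SAP A.5 and Protocol B.12:

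- State whether N=200 is per arm or the whole subgroup, and reconcile 375 with 450 per arm.
- Give power for the interaction contrasts at the expected subgroup sizes, with the assumed variance and interaction effect, or give the difference detectable with 80% power.
- Label 91/85/77% as power for an effect within one subgroup of that size, and stop calling it conservative for the interaction test.
- Delete the closing sentence on similar power.
- Commit to reporting subgroup rate ratios and their ratios with confidence intervals, and state that a non-significant interaction is not evidence of equal effect.

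The cost is one recalculation, one reworded paragraph in each document, and a less favourable stated power for an exploratory aim. Sample size, data collection and the planned models stay as they are.
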